7.2 Analysis Set

The pharmacodynamic analysis set will consist of subjects treated with at least 1 dose of IMP who have QT data at baseline and at least 1 postdose time point.

The safety analysis set will consist of subjects who received at least 1 dose of IMP and have postdose safety data.

7.3 Handling of Missing Data

No data imputation will be performed for missing data.

7.4 Primary and Secondary Endpoint Analyses

12-lead Holter ECG data will be used. For each parameter, the mean of measurements from 3 predose time points (1 hour, 30 minutes, and 15 minutes before IMP administration) in each period will be used as the baseline value. Changes from baseline in corresponding period will be calculated at each postdose time point.

7.4.1 Primary Endpoint Analyses

The primary endpoint is the time-matched difference between the OPC-61815 and placebo data in change from baseline for QTcF in 12-lead Holter ECG. Central tendency analysis for OPC-61815 will be performed for subjects in the pharmacodynamic analysis set who appropriately completed all IMP treatments (OPC-61815 16 mg, OPC-61815 32 mg, placebo, and moxifloxacin) (ie, in whom the administration of the injections was completed within the time windows presented in [Section 3.2 Trial Treatments without](#)

interruption after the first 30 minutes) and for whom predose and postdose QT data are available for all 4 treatment periods.

For each OPC-61815 dose (16 mg and 32 mg), the upper limit of the CI for the time-matched difference in the least squares mean for the change in QTcF from baseline compared to the placebo data will be evaluated to determine if it is lower than 10 msec at all postdose time points using the hypothesis presented below. Because the alternative hypothesis is an intersection hypothesis, the 2-sided 90% CI (1-sided 95%) will be calculated without type 1 error adjustment.

$$H_0: \bigcup \{ \mu_{A(i)} - \mu_{P(i)} \geq 10 \}, i = 1, 2, \dots, 8$$

$$H_1: \bigcap \{ \mu_{A(i)} - \mu_{P(i)} < 10 \}, i = 1, 2, \dots, 8$$

$\mu_{A(i)}$: Mean change from baseline in QTcF interval at time i after OPC-61815 administration

$\mu_{P(i)}$: Mean change from baseline in QTcF interval at time i after placebo administration

$i = 1, 2, \dots, 8$ respectively correspond to 1, 1.5, 2, 3, 4, 6, 12, and 24 hours after start of IMP administration

Using a linear mixed effect model with baseline QTcF in each treatment period as a covariate, treatment, sequence, treatment period, time point, and interaction between treatment and time point as fixed effects, and subject as a random effect, point estimates and CIs for the time-matched difference in the least squares mean for the change in QTcF from baseline compared to the placebo data will be calculated.

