3.8.3 Individual Subject Discontinuation

3.8.3.1 Treatment Discontinuation/Interruption During a Treatment Period

After the first dose of IMP, a subject may permanently stop or interrupt treatment during any of the treatment periods for a variety of reasons. Treatment discontinuation or interruption in any treatment period may be initiated by a subject or may become medically necessary due to AEs, required treatment with a prohibited medication or therapy, or for other reasons, as determined by the investigator or subinvestigator. Even when a subject discontinues or interrupts treatment during a treatment period, the subject may continue participation in the trial, if the investigator or subinvestigator decides that the subject is eligible for resuming treatment or receiving IMP for the remaining periods and if the subject is willing to continue the trial.

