3.8.3.2 Treatment Discontinuation (Withdrawal)

After the first dose of IMP, a subject may permanently stop treatment for a variety of reasons. Treatment discontinuations may be initiated by a subject or may become medically necessary due to AEs, required treatment with a prohibited medication or therapy, or for other reasons, as determined by the investigator or subinvestigator. Any subject who is unwilling to continue the trial after discontinuing treatment during a treatment period (see [Section 3.8.3.1](#)) must be withdrawn from the trial. Subjects who withdrew after the start of the IMP administration should be encouraged to complete all early termination (ET) assessments as soon as possible after withdrawal.

If any of the following AEs occur, the subject must be withdrawn from the trial for safety reasons after discontinuation of IMP:

- Occurrence of severe drug hypersensitivity
- Occurrence of severe AEs of special interest (feeling abnormal, feeling hot, erythema, hyperhidrosis, pruritus, rash, urticaria, nausea, epigastric discomfort, dyspnoea)
- AST or ALT ≥ 3 times the upper limit of normal (ULN)
- ≥ 12 mEq/L increase in serum sodium concentration within 24 hours of IMP administration compared to baseline
- A serum sodium concentration of ≥ 155 mEq/L

- Regarding 12-lead ECG findings the day before IMP administration (Day -1) in Periods 2, 3, and 4, QTcF interval of <320 msec or >450 msec observed in at least 2 of 3 ECG recordings performed 1 hour after preceding observation of QTcF interval in either range in at least 2 of 3 ECG recordings
- Regarding 12-lead ECG findings after start of IMP administration in each period, QTcF interval of >500 msec observed in an ECG recording 1 hour after preceding observation of QTcF interval in the same range (if a 12-lead ECG recording is originally scheduled 1 hour after the first recording, the scheduled test constitutes the re-examination.)

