6.3 Pharmacokinetic/Pharmacodynamic Methods

For subjects who have QT data and plasma OPC-61815 concentration data after administration of OPC-61815, as well as QT data after placebo administration at the matching time points, differences between OPC-61815 and placebo in change in QTcF interval from baseline at the matching time points are analyzed. A linear mixed-effects model is used, taking plasma OPC-61815 concentration as a fixed effect and subject as a random effect, to investigate the relationships between plasma OPC-61815 concentration and pharmacodynamic parameters.

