7.4.3 Assay Sensitivity Assessment

As an assay sensitivity assessment, moxifloxacin will be evaluated as a positive control using the same analysis set and statistical method as those stated in [Section 7.4.1 Primary Endpoint Analyses](#).

For moxifloxacin, the lower limit of the CI for the time-matched difference in the least squares mean for the change in QTcF from baseline compared to the placebo data will be evaluated if it is higher than 0 msec at any of the postdose time points using the hypothesis presented below. Because of the multiplicity arising from assay sensitivity assessments at 5 postdose time points (1, 1.5, 2, 3, and 4 hours), type 1 error adjustment will be performed using the Bonferroni method, and the 2-sided 98% (1-sided 99%) CI will be calculated.

$$H_0: \bigcap \{ \mu_{M(i)} - \mu_{P(i)} \leq 0 \}, i = 1, 2, \dots, 5$$

$$H_1: \bigcup \{ \mu_{M(i)} - \mu_{P(i)} > 0 \}, i = 1, 2, \dots, 5$$

$\mu_{M(i)}$: Mean change from baseline in QTcF interval at time i after moxifloxacin administration

$\mu_{P(i)}$: Mean change from baseline in QTcF interval at time i after placebo administration

$i = 1, 2, \dots, 5$ respectively correspond to 1, 1.5, 2, 3, and 4 hours after IMP administration

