11.1 Primary and Secondary Endpoint Analyses

11.1.1 Primary Endpoint Analyses

The primary endpoint is the time-matched difference between the OPC-61815 and placebo data in change from baseline for QTcF in 12-lead Holter ECG. Central tendency analysis for OPC-61815 will be performed for subjects in the pharmacodynamic analysis set who appropriately completed all IMP treatments (OPC-61815 16 mg, OPC-61815 32 mg, placebo, and moxifloxacin) (ie, in whom the administration of the injections was completed within the time windows presented in Protocol 3.2 Trial Treatments [the duration of intravenous administration of OPC-61815 16 mg or 32 mg or placebo: 59 to

65 minutes] without interruption of administration from 30 minutes after the start, as well as the condition described in 7.4 Treatment Compliance) and for whom predose and postdose QT data are available for all 4 treatment periods.

For each OPC-61815 dose (16 mg and 32 mg), the upper limit of the CI for the time-matched difference in the least squares mean for the change in QTcF from baseline compared to the placebo data will be evaluated to determine if it is lower than 10 msec at all postdose time points using the hypothesis presented below. Because the alternative hypothesis is an intersection hypothesis, the 2-sided 90% CI (1-sided 95%) will be calculated without type 1 error adjustment.

$$H_0: \bigcup \{\mu_{A(i)} - \mu_{P(i)} \geq 10\}, i = 1, 2, \dots, 8$$

$$H_1: \bigcap \{\mu_{A(i)} - \mu_{P(i)} < 10\}, i = 1, 2, \dots, 8$$

$\mu_{A(i)}$: Mean change from baseline in QTcF interval at time i after OPC-61815 administration

$\mu_{P(i)}$: Mean change from baseline in QTcF interval at time i after placebo administration
 $i = 1, 2, \dots, 8$ respectively correspond to 1, 1.5, 2, 3, 4, 6, 12, and 24 hours after start of IMP administration

Using a linear mixed effect model with baseline QTcF in each treatment period as a covariate, treatment, sequence, treatment period, time point, and interaction between treatment and time point as fixed effects, and subject as a random effect, point estimates and CIs for the time-matched difference in the least squares mean for the change in QTcF from baseline compared to the placebo data will be calculated.

SAS code is shown below. The data set will include all 4 treatments data.

```
proc mixed method=reml;  
  class treatment subject time arm period;  
  model change = arm period treatment time treatment*time baseline/ s ddfm=satterth;  

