  random subject(arm);  
  lsmeans treatment*time/diff pdiff cl alpha=0.1;  
run;
```

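### The 10 msec QTcF test and the assay sensitivity test keep only compliant completers of all four treatments; this discards valid periods and can bias towards no effect

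*Protocol*

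**What the plan says.** Protocol 7.4.1 and SAP 11.1.1 confine the central tendency analysis to members of the pharmacodynamic set "who appropriately completed all IMP treatments (OPC-61815 16 mg, OPC-61815 32 mg, placebo, and moxifloxacin") and "for whom predose and postdose QT data are available for all 4 treatment periods". Completion includes infusion compliance: 59 to 65 minutes, with no interruption once 30 minutes have passed. SAP 7.4 adds receipt of the full dose. Protocol 7.4.3 assesses moxifloxacin "using the same analysis set and statistical method as those stated in" 7.4.1, and SAP 11.1.3 agrees.

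Other provisions that bear on this:

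- Protocol 3.8.3.1: "Even when a subject discontinues or interrupts treatment during a treatment period, the subject may continue participation in the trial", if the investigator agrees and the subject is willing.
- Protocol 3.8.3.2 makes withdrawal mandatory after a postdose "QTcF interval of >500 msec observed in an ECG recording 1 hour after preceding observation of QTcF interval in the same range". A separate Day -1 rule for Periods 2 to 4 is two-sided: "QTcF interval of <320 msec or >450 msec observed in at least 2 of 3 ECG recordings", again with confirmation.
- Protocol 3.3.1: a subject withdrawn after allocation is not replaced. Protocol 7.3: nothing is imputed.
- SAP 11.1.1 fits PROC MIXED with a random subject term ("random subject(arm)").
- The categorical and descriptive ECG analyses use the full pharmacodynamic set (Protocol 7.4.2). The concentration-QTc model takes subjects with OPC-61815 data "as well as QT data after placebo administration at the matching time points" (Protocol 6.3).

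No analysis of the 10 msec criterion on all available periods appears in the text. The contents of SAP Appendices 2 and 3, which list tables and listings, were not available.

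**The concern.** The restriction works per subject, while each test is a contrast between two treatments. A man with valid 16 mg, 32 mg and placebo periods leaves both OPC-61815 contrasts if he misses only moxifloxacin. A man with one late interruption of an infusion may stay in the trial under 3.8.3.1 and be dosed and recorded in later periods, which both tests then ignore. SAP section 10 treats the same non-compliance differently for pharmacokinetics: it drops only the affected period.

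Two things are at stake.

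- **Precision.** The 5% allowance in the sample size is for discontinuation. The rule also removes whole subjects for one out-of-window infusion, one late interruption or one missing period.
- **Direction.** Among the withdrawal rules, only the confirmed postdose rule above 500 msec is clearly tied to prolongation. If it is met on OPC-61815 in Periods 1 to 3, the subject leaves the primary test because his QTcF rose. That lowers the estimated effect and is anti-conservative for a claim that the upper limit is below 10 msec. The Day -1 rule is two-sided and follows washout, so it has no fixed direction.

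**Working it through.** **Inputs from Protocol 7.1 and 7.4.** Within-subject SD 7.86 msec; OPC-61815 effect 3.0 msec; margin 10 msec; one-sided 5% at 8 time points for 2 doses; moxifloxacin effect 9.6 msec at one-sided 1%; required 45 and 21; 48 enrolled.

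**1. Reproducing the plan's figures.** The standard error of a paired difference is 7.86 × √(2/n), with n − 1 degrees of freedom (noncentral t) and a distance to the margin of 10 − 3 = 7 msec. Joint power of 90% over 8 × 2 = 16 independent comparisons needs 0.9^(1/16) = 0.9934 per comparison, which gives n = 45. For moxifloxacin, 90% at a single time point gives n = 21. With 5% discontinuation, 45/0.95 = 47.4, so 48. All three figures are reproduced, so the sample size itself is not in error.

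**2. Power as evaluable subjects are lost** (same formula, 16th power):

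| Evaluable | SE (msec) | Power per comparison | Joint power |
|---|---|---|---|
| 48 | 1.604 | 0.9960 | 93.8% |
| 45 | 1.657 | 0.9940 | 90.9% |
| 44 | 1.676 | 0.9932 | 89.6% |
| 42 | 1.715 | 0.9911 | 86.6% |

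The plan can lose three subjects. If 5% are lost for any reason, the binomial chance of at least 45 evaluable is 78%; at an assumed 10% it is 28%.

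**3. What the discarded periods are worth.** Generalised least squares with 44 completers plus 4 subjects who each lack one period (ICC 0.1 to 0.5), against 89.6% with the 44 alone:

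- moxifloxacin missing: SE 1.604 for both doses, joint power about 94%;
- 16 mg missing: SE 1.642 for 16 mg and 1.604 for 32 mg, about 93%;
- placebo missing: SE 1.642 for both doses, about 92%.

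**4. Bias from one subject withdrawn on 32 mg.** Assumed: 45 completers on a four-sequence Williams square, residual SD 7.86, ICC 0.3, and a REML fit of the planned model structure without the baseline covariate, over 300 simulated data sets. The rise in QTcF is either flat over all eight time points or falls linearly over them to zero at 24 hours. The completers' upper limit is 3 + 1.646 × 7.86 × √(2/45) = 3 + 2.73 = 5.73 msec. Mean increase in the 1-hour upper limit when he is included (flat / decaying, msec):

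| Withdrawn after | +50 | +80 | +100 |
|---|---|---|---|
| Period 1 | 0.09 / 0.61 | 0.07 / 1.01 | 0.05 / 1.30 |
| Period 2, no placebo period | 0.65 / 0.83 | 1.20 / 1.43 | 1.61 / 1.85 |
| Period 3, with placebo period | 1.19 / 1.05 | 2.03 / 1.82 | 2.73 / 2.34 |

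The decision rests on the largest of the eight limits. At +80 that rises by 0.05 / 0.33, 1.18 / 0.76 and 2.04 / 1.08 respectively. ICC values of 0.1 and 0.5 agree within about 0.1 msec, and adding a baseline covariate (assumed slope −0.3) changes the +80 results by at most about 0.04.

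**5. When the conclusion flips.** At the planned effect, 5.73 + 2.73 = 8.46 msec in the worst case, which still passes. A simple paired illustration nearer the margin: 47 subjects at 7 msec give 7 + 2.72 = 9.72 (pass). Adding one at 60 msec gives a mean of (47 × 7 + 60)/48 = 8.10 and a limit of 8.10 + 2.69 = 10.8 (fail), with the SD held at 7.86.

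**The case against.** The strongest reply is that the bias route is remote. It needs a confirmed value above 500 msec on the single safety ECG, not on the Holter endpoint, in men screened against QTcF above 450 msec. It must occur on OPC-61815 and before Period 4, since a compliant subject who meets the rule in Period 4 has already had all four treatments. The documents give no rate. A flat rise to 24 hours is also unlikely for a drug whose half-life is stated as under 3 hours, so the decaying figures are the more realistic ones. After a flat rise in Period 1 the random subject term absorbs nearly all of it, and including the subject moves the 1-hour limit by less than 0.1 msec. All of this stands and limits the size of the problem.

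Such a subject would also not be hidden. Holter outliers are counted in the full pharmacodynamic set, and SAP 7.1 reports how many subjects enter the central tendency analysis. That is true, but neither those tables nor the concentration-QTc model applies the 10 msec criterion.

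On precision, pooled model degrees of freedom (about 31n) give 91.3% at 44 and 88.7% at 42, and power for one dose alone is 91.0% at 40. These readings move the point where power drops below 90%. They depart from the n − 1, 16-comparison basis that reproduces the plan's 45.

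Assay sensitivity is not at risk on power: single-time-point power is 99.6% at 36. Losing moxifloxacin prolongers is conservative there. Finally, 3.8.3.1 governs participation, so it does not contradict 7.4.1; it does mean that usable periods will be collected and left out.

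**Conclusion.** The concern holds, and the restriction should be changed. Both tests discard valid periods that the planned model can use, and neither document gives a reason for doing so. The usual cost is precision: joint power drops below 90% from the fourth excluded subject on the plan's own basis. The less likely but more serious cost is an exclusion that depends on the outcome and favours a negative QT conclusion. One such subject is worth 0.05 to 2.7 msec on the 1-hour upper limit. For a decaying +80 msec rise, the deciding limit moves by 0.3 to 1.1 msec. This does not overturn a result at the planned 3 msec effect. It can when the completers' limit lies within about 1 to 2 msec of 10, or up to 2.7 in the extreme flat +100 case. The bias figures rest on assumed rises, ICC and sequence layout; the power figures rest on the plan's SD and its independence assumption.

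**What to change.** In Protocol 7.4.1 and SAP 11.1.1, fit the same PROC MIXED model in the pharmacodynamic analysis set and define inclusion by period, for example: a treatment period is included if it has a baseline QTcF, at least one postdose QTcF, and dosing in that period that meets SAP 7.4. Under-dosed infusions then still cannot dilute an OPC-61815 effect. Use the same set for assay sensitivity (Protocol 7.4.3, SAP 11.1.3), and keep the four-treatment completer analysis as a sensitivity analysis. At minimum, keep the completer set as primary and prespecify the all-available-period analysis as the sensitivity analysis. In either case, list every excluded subject or period with its reason, treatment and QTcF values.

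The cost is wording in two documents and one listing; the model code is unchanged. The downsides are slight imbalance and reliance on missing at random for periods never received. An infusion stopped early still stays outside the model and would be visible only in the listing.

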7.4.2 Secondary Endpoint Analyses

Analyses described in the subsequent sections will be performed per treatment in the pharmacodynamic analysis set.

7.4.2.1 Categorical Analysis

The number and percentage of subjects who fulfilled the following criteria for QTcF interval at least once after IMP administration are calculated. The same calculation will also be performed at each time point.

- 1) Prolongation of absolute QTc interval:
 - QTc interval >450 msec

- QTc interval >480 msec
 - QTc interval >500 msec
- 2) Change from baseline in QTc interval:
- >30 msec increase in QTc interval from baseline
 - >60 msec increase in QTc interval from baseline

7.4.2.2 Electrocardiogram (12-lead Holter ECG)

For each parameter, descriptive statistics will be calculated for measurements and changes from baseline at each time point. A shift table of normal/abnormal assessments at each postdose time point compared to baseline will also be created. A frequency distribution of each waveform pattern will be drawn.

7.4.3 Assay Sensitivity Assessment

As an assay sensitivity assessment, moxifloxacin will be evaluated as a positive control using the same analysis set and statistical method as those stated in [Section 7.4.1 Primary Endpoint Analyses](#).

For moxifloxacin, the lower limit of the CI for the time-matched difference in the least squares mean for the change in QTcF from baseline compared to the placebo data will be evaluated if it is higher than 0 msec at any of the postdose time points using the hypothesis presented below. Because of the multiplicity arising from assay sensitivity assessments at 5 postdose time points (1, 1.5, 2, 3, and 4 hours), type 1 error adjustment will be performed using the Bonferroni method, and the 2-sided 98% (1-sided 99%) CI will be calculated.

$$H_0: \bigcap \{ \mu_{M(i)} - \mu_{P(i)} \leq 0 \}, i = 1, 2, \dots, 5$$

$$H_1: \bigcup \{ \mu_{M(i)} - \mu_{P(i)} > 0 \}, i = 1, 2, \dots, 5$$

$\mu_{M(i)}$: Mean change from baseline in QTcF interval at time i after moxifloxacin administration

$\mu_{P(i)}$: Mean change from baseline in QTcF interval at time i after placebo administration

$i = 1, 2, \dots, 5$ respectively correspond to 1, 1.5, 2, 3, and 4 hours after IMP administration

7.5 Analysis of Demographic and Baseline Characteristics

Frequency distribution or descriptive statistics will be calculated for baseline characteristics per sequence and as a whole in the pharmacodynamic analysis set and safety analysis set.

7.6 Safety Analysis

Tabulations discussed in the subsequent sections will be performed per treatment in the safety analysis set.

7.6.1 Adverse Events

All AEs will be coded by system organ class and preferred term of the Medical Dictionary for Regulatory Activities (MedDRA). The incidence of the following events will be summarized:

- TEAEs
- TEAEs by severity
- TEAEs with an outcome of death
- Serious TEAEs
- TEAEs leading to discontinuation of IMP

When the same AE occurs more than once during one treatment period in the same subject, the most severe event is included in incidence calculation. The incidence of TEAEs potentially causally related to IMP will also be summarized.

In Periods 1, 2, and 3, TEAEs are the events occurring after the start of IMP administration in each period until the start of IMP administration in the subsequent period. In Period 4, AEs that occur after the start of IMP are recorded as TEAEs.

7.6.2 Clinical Laboratory Data

For clinical laboratory data other than qualitative urine tests, descriptive statistics will be calculated for measurements and changes from baseline at each postdose time point. For qualitative urine test data, a shift table comparing test results at each postdose time point to baseline will be created. Each clinical laboratory test result other than qualitative urine tests will be categorized into “within normal,” “below the lower limit of normal,” and “above the upper limit of normal” using the trial site’s reference range to create a shift table of test results at each postdose time point compared to baseline.

7.6.3 Vital Signs and Body Weight

Descriptive statistics will be calculated for measurements and changes from baseline at each postdose time point.

7.6.4 12-lead Electrocardiogram Data

For each parameter, descriptive statistics will be calculated for measurements and changes from baseline at each postdose time point. On normal/abnormal assessment, a shift table comparing data at each postdose time point to baseline will be created.

